5.2.5. Physical Examination

Physical examination is conducted during screening, on Day 1 of each cycle, and at the post-treatment visit. Abnormal findings in PE were to be reported as AEs. These data will not be summarized, i.e. they will only be available in listings.

5.2.6. Tumor Responses and Clinical Benefit

For tumor assessment, all sites of disease will be assessed radiologically by CT or MRI at screening, every other cycle while on treatment and every 2 months in survival followup, until the date of (i) disease progression as defined by RECIST 1.1 ([Eisenhauer et al, 2009](#)) or by clinical criteria; or (ii) withdrawal of consent; or (iii) receiving subsequent anti-cancer therapy, whichever is earlier. At each tumor assessment visit, the overall visit response by RECIST will be determined three ways: (1) derived programmatically using the information from target lesions (TL), non-target lesions (NTLs) and new lesions as entered into the eCRF, (2) by the investigator and collected in the eCRF and (3) by Blinded Independent Central Review (BICR) which is described in the Independent Review Charter.

For all patients, the RECIST tumor response data will be used to determine each patient's visit response according to RECIST version 1.1 and the best overall response (BOR).

5.2.6.1. Target Lesions (TLs)

Measurable disease is defined as having at least one measurable lesion which is

- $\geq 10\text{ mm}$ in the longest diameter (LD) (except lymph nodes which must have short axis $\geq 15\text{ mm}$) with computed tomography (CT) or magnetic resonance imaging (MRI); or
- $\geq 10\text{ mm}$ caliper measurement by clinical exam (lesions which cannot be accurately measured with calipers should be recorded as non-measurable); or
- $\geq 20\text{ mm}$ by chest X-ray.

Previously irradiated lesions (or lesions treated with loco-regional therapies) may be considered measurable if unequivocal growth of the lesion has been demonstrated. A patient can have a maximum of 5 measurable lesions representative of all involved organs (maximum of 2 lesions per organ, both the lymph node and skin will be considered as a single organ) recorded at baseline and these are referred to as target lesions. If more than one baseline scan is recorded then measurements from the one that is closest to start of treatment will be used to define the baseline sum of TLs. [Table 14](#) gives definition of TL visit responses.

Table 14 Definition of TL Visit Responses

Visit Responses	Description
Complete Response (CR)	Disappearance of all target lesions. Any pathological lymph nodes selected as target lesions must have a reduction in short axis to <10mm.
Partial response (PR)	At least a 30% decrease in the sum of diameters of target lesions, taking as reference the baseline sum of diameters as long as criteria for PD are not met.
Progressive disease (PD)	A $\geq 20\%$ increase in the sum of diameters of target lesions and an absolute increase of $\geq 5\text{mm}$, taking as reference the smallest sum of diameters (i.e. nadir) since treatment started including the baseline sum of diameters.
Stable disease (SD)	Neither sufficient shrinkage to qualify for PR nor sufficient increase to qualify for PD.

Rounding of TL data

For calculation of PD and PR for TLs percentage changes from baseline and previous minimum should be rounded to 1 decimal place before assigning a target lesion response. For example 19.95% should be rounded to 20.0% but 19.94% should be rounded to 19.9%.

Missing TL data

If any target lesion measurements are missing then the target lesion visit response is Not Evaluable (NE). The overall visit response will also be NE, unless there is a progression of non-target lesions or new lesions, in which case the response will be PD.

TL too small to measure

If a target lesion becomes too small to measure a value of 5mm will be entered into the database and used in TL calculations, unless the radiologist has indicated and entered a smaller value that can be reliably measured.

Lesions that split

If a TL splits, then the LDs of the split lesions should be summed and reported as the LD for the lesion that split.

Lesions that merge

If target lesions merge, then the LD of the merged lesion should be recorded for one of the TL sizes and the other TL size should be recorded as 0 cm.

Change in method of assessment of target lesions

CT, MRI and clinical examination are the only methods of assessment that can be used within a trial, with CT and MRI being the preferred methods and clinical examination only used in special cases. If a change in method of assessment occurs between CT and MRI this will be considered acceptable and no adjustment within the programming is needed.

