#### 11.5.3.1. Evaluation of Target Lesion Response

- **Complete response (CR):** Disappearance of all target lesions. Any pathological lymph nodes (whether target or nontarget) must have reduction in short axis to < 10 mm.
- **Partial response (PR):** At least a 30% decrease in the sum of diameters of target lesions, taking as reference the baseline sum of diameters.
- **Progressive disease (PD):** At least a 20% increase in the sum of diameters of target lesions, taking as reference the smallest sum on study (this includes the baseline sum if that is the smallest on study). In addition to the relative increase of 20%, the sum must also demonstrate an absolute increase of at least 5 mm. The appearance of 1 or more new lesions is also considered progression.
- **Stable disease (SD):** Neither sufficient shrinkage to qualify for PR nor sufficient increase to qualify for PD, taking as reference the smallest sum of diameters while on study.

A response category of not evaluable (NE) is to be used when there is inadequate information to otherwise categorize the response status.

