5.2.6.3. Time Point Response (TPR)

Table 16 defines how the previously defined TL and NTL visit responses will be combined with new lesion information to give a TPR. The possible TPRs at a visit are CR, PR, SD, PD, and NE.

Table 16 Evaluation of Time Point Response

Target Lesions	Non-target Lesions	New Lesions	Overall Response
CR	CR	No	CR
CR	Non-CR/Non-PD	No	PR
CR	Not evaluated	No	PR
PR	Non-PD/not all evaluated	No	PR
SD	Non-PD/not all evaluated	No	SD
Not all evaluated	Non-PD	No	NE
PD	Any	Yes or No	PD
Any	PD	Yes or No	PD
Any	Any	Yes	PD

CR = complete response, PR= partial response, SD = stable disease, PD = progressive disease, NE = not evaluable

At each visit, patients will be programmatically assigned a RECIST TPR of CR, PR, SD, PD or NE depending on the status of their disease compared to baseline and previous assessments as discussed in the [Sections 5.2.6.1 and 5.2.6.2](#).

For a scheduled tumor scan assessment, it is expected that there will be a variation for the actual timing of scans among target, non-target, and new lesions. In assigning a date for the derived overall assessment at a visit, the earliest date collected at that visit will be used

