5.2.7. Progression-free Survival

Since disease progression is assessed periodically, PD can occur any time in the time interval between the last assessment where PD was not documented and the assessment when PD is documented.

Hence, progression-free survival (PFS) is defined as the time (months) from date of first dose date of study drug for patients in Part 1 or date of randomization for patients in Part 2 until date of documented disease progression or death due to any cause, whichever comes first. More specifically, PFS will be determined using all the assessment data up until the last evaluable visit prior to or on the date of (i) disease progression as defined by RECIST 1.1 (Eisenhauer et al,

2009) or by clinical criteria (this will not apply to the BICR analysis); or (ii) withdrawal of consent; or (iii) receiving subsequent anti-cancer therapy, whichever is earlier.

PFS will be calculated using two response data sets: derived and BICR. For PFS determined by BICR, only progression per RECIST will be considered. For PFS as determined by derived, either clinical progression or progression by RECIST (whichever comes first) will be considered.

Death, regardless of cause, is always considered as a PD event. The detailed censoring rules for the analysis are summarized in [Table 18](#).

Table 18 Assignment of Progression or Censoring Based on Radiological Assessment

Situation	Date of Progression or Censoring	Outcome
No Baseline assessment	Date of first dose of study drug for patients in Part 1 or date of randomization for patients in Part 2	Censored
No progression	Date of last adequate radiological disease assessment	Censored
Treatment discontinuation for reasons other than disease progression	Date of last progression assessment with no documented progression	Censored
New anticancer treatment started prior to documented disease progression	Date of last adequate radiologic assessment no later than the initiation of new anticancer treatment	Censored
Disease progression	Date of the first reported progression	Progressed
Death without a PD	Date of death	Progressed
Investigator claim of clinical progression	Date of the investigator assigned PD	Progressed

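### Derived tumour response: absent non-target progression or a new lesion, a missing target-lesion measurement makes the visit NE even when the measured lesions already prove progression

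*SAP*

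**What the plan says.** SAP 5.2.6 determines the visit response in three ways: by program from the eCRF lesion data, by the investigator, and by blinded independent central review (BICR). The rules in 5.2.6.1 to 5.2.6.3 govern the first, the derived response.

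- **Missing data (SAP 5.2.6.1).** "If any target lesion measurements are missing then the target lesion visit response is Not Evaluable". The next sentence carries this to the visit: "The overall visit response will also be NE, unless there is a progression of non-target lesions or new lesions".
- **Combination table (SAP Table 16).** The matching row reads "Not all evaluated Non-PD No NE" (target lesions, non-target lesions, new lesions, overall response).
- **Progression.** Protocol 11.5.3.1 requires "At least a 20% increase in the sum of diameters of target lesions, taking as reference the smallest sum on study", and adds that "the sum must also demonstrate an absolute increase of at least 5 mm". SAP Table 14 uses the same two thresholds.
- **Meaning of NE.** Protocol 11.5.3.1 keeps NE for visits without enough information to assign another category. The corresponding row of Protocol Table 11-4 starts from a target-lesion response of NE, not from target lesions that were incompletely measured.
- **Use.** SAP 5.2.7 calculates PFS on the derived and the BICR responses only. Table 18 has a censoring row headed "New anticancer treatment started prior to documented disease progression".

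**The concern.** The missing-data rule looks only at whether the set of measurements is complete. It does not ask whether those present already settle the answer. When they do, NE is the wrong category under SAP Table 14 and under the protocol's own meaning of NE. The Table 16 row that maps a target-lesion PD to an overall PD cannot help, because the missing-data rule stops the target-lesion response from ever being PD.

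What is at stake is the date, and sometimes the existence, of a progression event in derived PFS, together with derived duration of response and best overall response. A later scan may not correct the error. Scans run only until progression (Protocol 6.1.5), and study drug stops on radiologically documented progression (Protocol 12.3). An investigator who sees clear growth on the measured lesions may therefore end both treatment and scanning.

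**Working it through.** **Inputs**
- PD thresholds: at least 20% and at least 5 mm above the smallest sum (SAP Table 14, Protocol 11.5.3.1).
- Percentages rounded to one decimal before classification (SAP 5.2.6.1).
- Scan interval: every two 21-day cycles on treatment, then 60 ± 7 days (Protocol 6.1.5).
- Assumption: the nadir is a full sum, from a visit with every target lesion measured.

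**Step 1. The plan's rounding example.** 19.95% rounds to 20.0% and 19.94% to 19.9%, as the SAP states.

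**Step 2. Lower bound.** Let N be the nadir sum, P the sum of the measured lesions and M ≥ 0 the missing diameter. The full sum is P + M ≥ P. If P − N ≥ 5 mm and 100 × (P − N)/N rounds to at least 20.0%, then P + M meets both conditions for every M. In 200,000 simulated visits, 141,381 met PD on the partial sum, and none of these failed PD on the full sum. That count reflects the simulated sizes and is not a trial frequency.

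**Step 3. Illustration** (assumed sizes: N = 50 mm, two target lesions, one not measured)

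| Measured lesion | Increase over N | Is PD certain? | SAP rule | With exception |
|---|---|---|---|---|
| 62 mm | 12/50 = 24.0%, 12 mm | yes | NE | PD |
| 60 mm | 10/50 = 20.0%, 10 mm | yes | NE | PD |
| 59 mm | 9/50 = 18.0%, 9 mm | no | NE | NE |

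**Step 4. Delay if the next scan records PD.** On treatment, 2 × 21 = 42 days. In follow-up, 60 − 7 = 53 to 60 + 7 = 67 days.

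**Step 5. Censoring.** If new therapy starts before PD is recorded, Table 18 censors at the last adequate radiologic assessment no later than that start. The note to Table 18 defines adequate by the investigator's response (CR, PR, SD or PD). If the investigator called the affected visit PD, that visit can itself become the censoring date in derived PFS. If the investigator also recorded NE, an earlier assessment is used.

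**Step 6. How demanding the condition is.** Assume k target lesions of equal size at nadir, one of them missing. The other k − 1 must total 1.2N, so each must reach 1.2k/(k − 1) times its nadir size:
- k = 2: 2.4 times, growth of 140%
- k = 3: 1.8 times, growth of 80%
- k = 5: 1.5 times, growth of 50%

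The 20% threshold governs when N is 25 mm or more; below that, the 5 mm threshold asks for more. With a single target lesion there is no partial sum and NE stands.

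**The case against.** Four points limit the finding, and all of them stand.

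- **Scope.** A reader might infer that the trial's PFS as a whole is affected. The documents show this for the derived response only. BICR follows a charter that is not provided, and PFS is run on both sources. A visit with non-target progression or a new lesion is PD regardless.
- **Rescue routes.** A reader might infer that every such progression is late or lost. Derived PFS also counts investigator-claimed clinical progression and death (SAP 5.2.7), so some cases are recovered. The recovery is partial: Table 18 names clinical progression and does not say that an investigator's radiological PD on incomplete measurements counts. Nor is censoring always at the preceding scan (Step 5).
- **Size.** It is tempting to attach a rate, for instance 2 to 5% of the 70 randomised patients, or roughly 1 to 4. Neither document supports any figure, and zero is equally compatible. Several things must coincide: a missing measurement, strong growth in the remaining lesions, no new lesion, no non-target progression and no clinical progression claim. Lesions too small to measure do not trigger the rule: "If a target lesion becomes too small to measure a value of 5mm will be entered into the database".
- **Effect on conclusions.** The rule is the same in both arms, so a later curve within each arm gives no direction for the hazard ratio. The protocol lists PFS among the safety endpoints (13.5.1) and calls the study descriptive (13.2.3).

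None of this supplies a reason to return NE when PD is certain. No text in either document provides the exception.

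**Conclusion.** The point holds for the programmatically derived response, as a minor one. When the measured target lesions alone meet the PD thresholds against the full nadir sum, the SAP still returns NE unless non-target progression or a new lesion is present. That is stricter than the protocol's meaning of NE.

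For an affected patient, derived PFS can move by about 42 days on treatment or 53 to 67 days in follow-up, or the event can be censored. The error can delay or remove a progression but cannot create one. The number of affected patients is unknown and probably small. No bias in the treatment comparison is established, and nothing can be said about BICR PFS. The conclusion rests on the lower-bound argument, which needs only non-negative diameters and a complete nadir sum.

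**What to change.** Add to the missing-data rule in SAP 5.2.6.1: *unless the sum of the non-missing target lesions is already at least 20% and at least 5 mm above the nadir sum, in which case the target-lesion response is PD.* State that the nadir sum comes from visits with all target lesions measured. Amend the Table 16 row for incompletely evaluated target lesions so that NE applies only when this exception is not met.

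The cost is a short text change, one table row and one programming condition, with no new data. Visits where PD is uncertain, such as the 59 mm example, stay NE. The change should be made before unblinding.

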5.2.6.2. Non-Target Lesions (NTLs) and New Lesions

The non-target lesion response will be based on the Investigator's overall assessment of NTLs as [Table 15](#):

Table 15 Definition of NTLs Visit Responses

Visit Responses	Description
CR	Disappearance of all NTLs present at baseline with all lymph nodes non-pathological in size (<10mm short axis).
PD	Unequivocal progression of existing NTLs, which may be due to an important progression in one lesion only or in several lesions
Non-CR/Non-PD	Persistence of one or more NTLs with no evidence of progression
NE	Only relevant when one or some of the NTLs have not been assessed and in the Investigator's opinion they are not able to provide an evaluable overall NTL assessment.

New lesions

New lesions will be identified via a Yes/No tick box. The absence and presence of new lesions at each visit should be listed alongside the TL and NTL visit responses.

A new lesion indicates progression so the overall visit response will be PD irrespective of the TL and NTL responses.

5.2.6.3. Time Point Response (TPR)

Table 16 defines how the previously defined TL and NTL visit responses will be combined with new lesion information to give a TPR. The possible TPRs at a visit are CR, PR, SD, PD, and NE.

Table 16 Evaluation of Time Point Response

Target Lesions	Non-target Lesions	New Lesions	Overall Response
CR	CR	No	CR
CR	Non-CR/Non-PD	No	PR
CR	Not evaluated	No	PR
PR	Non-PD/not all evaluated	No	PR
SD	Non-PD/not all evaluated	No	SD
Not all evaluated	Non-PD	No	NE
PD	Any	Yes or No	PD
Any	PD	Yes or No	PD
Any	Any	Yes	PD

CR = complete response, PR= partial response, SD = stable disease, PD = progressive disease, NE = not evaluable

At each visit, patients will be programmatically assigned a RECIST TPR of CR, PR, SD, PD or NE depending on the status of their disease compared to baseline and previous assessments as discussed in the [Sections 5.2.6.1 and 5.2.6.2](#).

For a scheduled tumor scan assessment, it is expected that there will be a variation for the actual timing of scans among target, non-target, and new lesions. In assigning a date for the derived overall assessment at a visit, the earliest date collected at that visit will be used

5.2.6.4. Best Overall Response (BOR)

BOR will be determined using TPRs up until the last evaluable TPR prior to or on the date of (i) disease progression as defined by RECIST 1.1 ([Eisenhauer et al, 2009](#)) or by clinical criteria (this will not apply to the BICR analysis); or (ii) withdrawal of consent; or (iii) receiving subsequent anti-cancer therapy, whichever is earlier.

A patient's BOR will be determined based on [Table 17](#). For data-driven scenarios which may not be covered by [Table 17](#), the BOR will be reviewed and determined by the medical advisors and statisticians prior to unblinding the study.

For patients who progress and subsequently have a response, the best overall response is only derived from assessments up to and including the time of the progression (i.e., it will not include the response after the patient has progressed).

There are two ways of assigning BOR for a patient when the minimum interval for confirmation of CR and PR is not satisfied or if there are no confirmatory scans for CR and PR:

- Adding two more response categories as: unconfirmed CR, unconfirmed PR;
- Assigning BOR as SD, that is, both the unconfirmed CR and unconfirmed PR will be SD.

Both ways of assigning BOR will be implemented.

The number and percentage of patients in each category of derived BOR (Confirmed CR, Confirmed PR, SD, PD, or NE) will be summarized.

Table 17 Best Overall Response When Confirmation of CR and PR are Required [a]

First TPR	Second TPR	Best overall response*^ for ORR	Best Overall Response for ORR _{UNCONFIRMED}
CR	CR	CR	CR
CR	PR	SD [b] or PD	Unconfirmed CR
CR	SD	SD [b] or PD	Unconfirmed CR
CR	PD	SD [b] or PD	Unconfirmed CR
CR	NE or NA	SD [c] or NE or NA	Unconfirmed CR
PR	CR	PR	Unconfirmed CR
PR	PR	PR	PR
PR	SD	SD [d]	Unconfirmed PR
PR	PD	SD [b] or PD	Unconfirmed PR
PR	NE or NA	SD [c] or NE or NA	Unconfirmed PR
NE	NE	NE	NE
NE	CR	SD	Unconfirmed CR
NE	PR	SD	Unconfirmed PR
NE	SD	SD	SD
NE or NA	PD	PD	PD
SD	PD	SD [b] or PD	SD [b] or PD
SD	CR	SD	SD
SD	PR	SD	SD
SD	SD	SD	SD
SD	NE or NA	SD [c] or NE or NA	SD [c] or NE
PD	No further evaluation	PD	PD

CR = complete response, PR= partial response, SD = stable disease, PD = progressive disease, NE = not evaluable, NA = not available.

a. The minimum interval for confirmation of CR and PR is 4 weeks.

b. Best response will be SD if the first time point overall response is after 35 days on study. Otherwise, the best response will be PD.

- c. Best response will be SD if the first time point overall response is after 35 days on study. Otherwise, the best response will be NE.
- d. Best response will be SD provided the criteria for PD have not been met from the first to second assessment.
- * A best overall response of SD can only be made after the subject is on study for a minimum of 35 days (counted from Cycle 1 Day 1). If the subject is on study for less than 35 days, any tumor assessment indicating stable disease before this time period will have a best response of NE unless PD is identified.
- ^Subsequent documentation of a CR may provide confirmation of a previously identified CR even with an intervening NE (e.g., CR NE CR). Subsequent documentation of a PR may provide confirmation of a previously identified PR even with an intervening NE or SD (e.g., PR NE PR or PR SD PR). However, only one (1) intervening NE or SD will be allowed between PRs for confirmation. Note: in the following scenario, PR SD NE PR, the second PR is not a confirmation of the first PR.

Objective response rate (ORR) will be calculated using two methods:

Method #1: ORR will be calculated using a strict interpretation of RECIST v1.1. Objective response will be derived as no/yes (0/1) variable. Patients with a BOR of confirmed CR or PR will be assigned 'Yes'. Patients not having a BOR of confirmed CR or PR will be assigned 'No'. Hence, ORR is defined as the proportion of patients with objective response being "Yes".

Method #2: ORR_{UNCONFIRMED} will be calculated using all responses regardless of confirmation. Objective response will be derived as no/yes (0/1) variable. Patients with a BOR of confirmed CR, confirmed PR, unconfirmed CR or unconfirmed PR will be assigned "Yes". All patients with other BOR values will be assigned "No". Hence, ORR_{UNCONFIRMED} is defined as the proportion of patients with objective response being "Yes".

Duration of Response (DOR) is the time between first response by RECIST of CR or PR and the first date that progressive disease is documented by RECIST (or clinical progression for investigator or derived analyses, whichever comes first) or death. Patients who do not experience PD or death will be censored at the last tumor assessment date. Only those patients with confirmed responses will be included in this analysis. Censoring will follow the rules outlined below for PFS in [Section 5.2.7](#).

Clinical benefit rate (CBR) is defined as the proportion of patients with a BOR of confirmed CR, confirmed PR, or SD.

ORR, ORR_{UNCONFIRMED}, DOR and CBR will be calculated using the derived responses, BICR responses, and investigator responses.

ORR, ORR_{UNCONFIRMED}, DOR and CBR will be summarized for Part 1, Part 2, and Part 1 + Part 2 patients treated with 240mg/m².

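### SAP Table 17 scores stable disease followed by an unconfirmed response as SD in the unconfirmed-ORR column, contradicting the Method #2 rule that the column implements

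*SAP*

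**What the plan says.** SAP 5.2.6.4 gives two ways to assign best overall response (BOR) when a CR or PR lacks a confirming scan, and says that both will be carried out. The first is "Adding two more response categories as: unconfirmed CR, unconfirmed PR". The second is "Assigning BOR as SD, that is, both the unconfirmed CR and unconfirmed PR will be SD".

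Two response rates follow. Method #1 counts confirmed responses only. Method #2, unconfirmed ORR, "will be calculated using all responses regardless of confirmation". Its scoring rule is explicit: "Patients with a BOR of confirmed CR, confirmed PR, unconfirmed CR or unconfirmed PR will be assigned" Yes, and "All patients with other BOR values will be assigned" No. SD therefore scores No.

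The link between scans and BOR is Table 17: "A patient's BOR will be determined based on" that table. It lists pairs of first and second time-point responses (TPRs), with one output column for ORR and one for unconfirmed ORR. Sequences the table does not cover go to the medical advisors and statisticians for a decision before unblinding.

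**The concern.** The two output columns appear to carry the two conventions: collapse to SD in the ORR column, separate unconfirmed categories in the unconfirmed-ORR column. The rows for SD then CR and SD then PR break that pattern. They show SD in both columns, so the collapse-to-SD result sits in the column meant to keep unconfirmed responses visible.

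The sequence is an ordinary one. Scans follow every even cycle (Protocol 6.1.5), so a patient can be stable after Cycle 2 and first respond after Cycle 4. If no confirming scan at least 4 weeks later is obtained before the BOR cutoff, that patient is lost from the one analysis designed to include unconfirmed responders. A programmer working from Method #2 and one working from Table 17 would report different rates. The difference would carry through the derived, investigator and BICR versions, and through the Part 1, Part 2 and pooled 240 mg/m² summaries.

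**Working it through.** The plan states no figure for this rule, so there is nothing to reproduce. The check compares every Table 17 row with the Method #2 scoring rule.

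**Step 1: count the rows.** Table 17 has 21 rows. Those with a CR or PR at either time point are five starting with CR, five starting with PR, two starting with NE and two starting with SD: 5 + 5 + 2 + 2 = 14.

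**Step 2: score the unconfirmed-ORR column.**

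| First TPR | Second TPR | Entry in unconfirmed-ORR column | Method #2 |
|---|---|---|---|
| CR | CR | CR | Yes |
| CR | PR, SD, PD, or NE/NA (4 rows) | Unconfirmed CR | Yes |
| PR | CR | Unconfirmed CR | Yes |
| PR | PR | PR | Yes |
| PR | SD, PD, or NE/NA (3 rows) | Unconfirmed PR | Yes |
| NE | CR | Unconfirmed CR | Yes |
| NE | PR | Unconfirmed PR | Yes |
| SD | CR | SD | **No** |
| SD | PR | SD | **No** |

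Yes: 1 + 4 + 1 + 1 + 3 + 1 + 1 = 12. No: 2. Only the two SD-first rows conflict with the rule.

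**Step 3: compare within the column.**
- The NE-first rows read "NE CR SD Unconfirmed CR" and "NE PR SD Unconfirmed PR". The same second-scan response counts after a non-evaluable scan but not after an evaluable stable one.
- PR then SD counts as Unconfirmed PR, but SD then PR does not. The same two readings score differently by order. Even PR then PD counts.

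**Step 4: look for text that rescues the rows.** The review before unblinding is for sequences outside the table, and both of these are listed. The footnotes deal with the 35-day minimum, with progression and with what confirms a response. None gives a reason to drop a response that follows SD.

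**Step 5: direction and size.** Both entries turn a response into a non-response, so the error can only be downward. SAP 2.3 plans 70 patients at 1:1, or 70/2 = 35 per arm. One affected patient moves that arm by 1/35 = 2.9 points, and k patients by k × 2.9. A denominator below 35, as the response evaluable set may have, makes each patient's share slightly larger. The documents give no value for k.

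**Step 6: after correction.** With the two cells changed, 14 of 14 response-containing rows score Yes. The ORR column does not change.

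**The case against.** The strongest reply is that Table 17 need not stop at the first two scans. BOR uses all TPRs up to the cutoff, and one footnote handles three- and four-scan sequences. Read pair by pair, a PR after SD would next be judged by the PR row with SD, PD or NE/NA as the second reading. Each of those gives Unconfirmed PR, so nothing would be lost. That is a reasonable guess at the intent, but the SAP does not say so. The footnote concerns confirmation only, and the two cells would still contradict Method #2.

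The second reply, that little depends on this endpoint, stands. SAP 6.2.8.7 assigns the stratified exact CMH comparison and its 80% CI to ORR, and the Clopper-Pearson intervals to ORR and CBR. Unconfirmed ORR is a descriptive supplement. The opportunity for error is also limited: confirmatory scans are required, non-progressors have a post-treatment scan, and imaging then continues every 2 months until progression.

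A reader might infer that a patient with SD, PR, PR would count in confirmed ORR but not in unconfirmed ORR. The documents do not support this. If only the first two scans are used, the SD-then-PR row gives SD in both columns. If later scans are used, the patient has a confirmed PR, which Method #2 scores Yes.

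**Conclusion.** The contradiction is real. Two of the 14 response-containing rows in Table 17 oppose the rule they implement. Applied as written, the table makes a patient whose first response follows SD and is never confirmed a non-responder in unconfirmed ORR.

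The size is 2.9 percentage points per affected patient in a Part 2 arm, assuming 35 patients in the denominator. It is zero if there are no such patients or if the programmers apply the pair-by-pair reading. A reader might want to put a total on the understatement, but any percentage of patients assumed affected simply returns itself as the answer. Nor do the documents show a difference between arms, since the rule is the same in both.

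Confirmed ORR and its Part 2 comparison, duration of response (confirmed responders only), PFS and OS do not use these cells. This is a definite but contained error in a supplementary summary, worth correcting because the correction is nearly free.

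**What to change.** 1. In the last column of Table 17, change SD then CR to Unconfirmed CR, and SD then PR to Unconfirmed PR, matching the NE-first rows. Leave the ORR column and the 35-day footnotes alone.
2. Add one sentence: unconfirmed ORR uses the best time-point response over all TPRs up to the cutoff already in SAP 5.2.6.4, namely the earliest of progression, withdrawal of consent and subsequent anti-cancer therapy. All three limits must be named, so that the sentence does not create a new mismatch. It also settles how a two-scan table applies to longer sequences.

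The cost is two cells and one sentence, made before unblinding, plus a matching check in the response-derivation program. No new data and no design change are needed.
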